4.2 Inclusion criteria

In order to be eligible to participate in this study, a patient must meet all of the following criteria:

- 1. Patient with melanoma, NSCLC or urogenital cancers ≥ 2 years since treatment with at least one cycle of immune checkpoint inhibitor (CTLA-4 inhibitor, PD-(L)1 inhibitor, or both) within the Department of Medical Oncology or Pulmonary Oncology of the UMCG.
- 2. Age ≥18 years at time of immune checkpoint inhibitor treatment
- 3. Understand or abide to the study procedures
- 4. Have given informed consent

A caregiver must meet all of the following criteria:

- 1. Age ≥18 years
- 2. Understand or abide to the study procedures
- 3. Have given informed consent

The inclusion criteria of the earlier study with this cohort have been adapted to this study.

4.3 Exclusion criteria

A patient or caregiver who meets any of the following criteria will be excluded from participation in this study:

- 1. As previous or subsequent therapies, only surgery and palliative radiotherapy is allowed (excluding radiotherapy in the head-neck and brain region)
- 2. Previous treatment in the past ten years for malignancy other than melanoma (excluding non-melanoma skin cancer, cervical intra-epithelial neoplasia or carcinoma in situ of breast) (for patients: other than current malignancy)
- 3. History of ear-nose-throat disease or auto-immune disorder affecting taste, smell, mouth mucosa, or saliva production (for patients: before start ICI)
- 4. As previous or subsequent therapies, palliative radiotherapy for bone metastasis in the brain and head-and-neck region

The exclusion criteria of earlier studies with this cohort have been adapted to this study.

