4. STUDY POPULATION

4.1 Population (base)

The participants in this study will be derived from an existing cohort of 70-120 patients who have undergone ICI treatment and have not received other systemic treatment (METc 2018/158, clinicaltrials.gov NCT03946007). These patients have been previously included in a cross-sectional study in which health-related quality of life, neurocognitive function, endocrine function, cardiovascular risk, physical fitness, mood disorders, sexual problems, and work participation were investigated. Patients have survived two years or more after the first cycle of an immune checkpoint inhibitor for melanoma, NSCLC, or urogenital cancer. Furthermore, the quality of life of the caregivers of these patients was studied.

The participants of this previously performed study who have given permission to be approached again, will be asked to participate in this study. In addition, to complete the required number of participants, additional patients from the departments of Medical Oncology and Pulmonary Disease, who were not included in the previously mentioned cohort, but who meet the criteria for this study, will be invited to participate in the study. Furthermore, a part of the caregivers of these patients have also been included in this previously mentioned cohort and has given permission to be approached again. The caregivers will act as control group for practical purposes, as they often accompany the patient on the hospital appointments. Furthermore, caregivers tend to have the same basic characteristics as the patients, and therefore, these characteristics will be distributed more equally in both groups. If a patient has a new caregiver, this new caregiver can also be asked to participate in this study instead of the previously included caregiver. Patients can also participate if they don't have a caregiver. The caregivers of the additional patients will also be invited.

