4.4 Sample size calculation

It is expected that long-term taste and smell dysfunction are prevalent in 25% of the patients. As described in the introduction, taste changes were found in 24% of patients using immunotherapy(9). In this study, however, it is not reported whether these changes were reported spontaneously or were actively asked. It is therefore possible that the percentage of 24% will be even higher. From earlier studies in patients years after treatment of testis carcinoma or childhood cancer, it is know that about 25% of these (former) patients have long-term taste and smell changes(21,22). Based on this information, the percentage of 25% was determined.

As caregivers with a history of disorders affecting taste and smell will be excluded, it is expected that these dysfunctions are present in 5% of the caregivers. If so, the differences between the patient and control group of caregivers can be assessed in a cohort of in total 49+49=98 patients and caregivers with a 95% confidence level and a power of 80%.

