8. METHODS

8.1 Study parameters/endpoints

8.1.1 Main study parameter/endpoint

Taste and smell dysfunction measured using taste strips and Sniffin' Sticks in patients compared to caregivers.

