10. STATISTICAL ANALYSIS

This study aims to investigate the prevalence of taste and smell dysfunction in a predefined cohort of melanoma, NSCLC and urogenital cancer patients. Results will be reported as mean (standard deviation) and median (range) for parametric and non-parametric continuous variables, respectively. Categorical data will be presented as N and percentages.

Participants and their caregivers will be compared using Mann Whitney U test or independent T-test, depending on data distribution. For ordinal data, Chi-square tests will be performed. Correlations between perceived and objective taste and smell dysfunction will be studied with Pearson's rho or Spearman's rho, depending on data distribution.

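### The listed criteria do not address systemic anticancer therapy given together with the ICI, so added patients can differ from the cohort that section 4.1 describes and enter an unadjusted comparison

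*Combined protocol and SAP*

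**What the plan says.** Section 4.1 draws patients from two sources. The first is an existing cohort of 70-120 patients "who have undergone ICI treatment and have not received other systemic treatment". The second, used to reach the required number, is patients from two departments (Medical Oncology, Pulmonary Disease), described as those "who were not included in the previously mentioned cohort, but who meet the criteria for this study, will be invited to participate". The statement about other systemic treatment describes the first source; it is not a listed criterion.

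The listed criteria are in sections 4.2 and 4.3. Inclusion criterion 1 asks for "treatment with at least one cycle of immune checkpoint inhibitor (CTLA-4 inhibitor, PD-(L)1 inhibitor, or both") and does not require that no other systemic drug was given. Exclusion criterion 1 states: "As previous or subsequent therapies, only surgery and palliative radiotherapy is allowed", with radiotherapy to the head-neck and brain region excepted. Exclusion criterion 4 uses the same two time words. No criterion mentions therapy given at the same time as the ICI.

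The main endpoint (section 8.1.1) is "Taste and smell dysfunction measured using taste strips and Sniffin' Sticks in patients compared to caregivers". Section 10 plans: "Participants and their caregivers will be compared using Mann Whitney U test or independent T-test, depending on data distribution". Sections 10 to 10.2 contain no covariate, stratum or subgroup for other cancer treatment. Section 3 has medical history and medication use taken from the patient file, but no planned analysis uses them for this purpose.

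**The concern.** Staff screen on the listed criteria, not on a description of an earlier cohort. If *previous* and *subsequent* are measured from the ICI, an added patient who received another systemic anticancer drug in the same period breaks no listed rule, yet does not fit the section 4.1 description.

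Caregivers who meet the criteria will not have had that drug. Any lasting effect it has on taste or smell therefore falls on one side of the comparison only, and the planned tests cannot separate it. Section 4.4 gives a reason to take this seriously: it supports the expected patient rate with earlier studies after testis and childhood cancer, in which "about 25% of these (former) patients have long-term taste and smell changes". The reference list shows that one of these studied survivors given cisplatin-based chemotherapy. The protocol thus relies on evidence of lasting change after other cancer treatment while leaving such treatment unaddressed when given alongside the ICI. At stake are the meaning of the patient prevalence, which could describe a mixed-treatment group, and part of the patient-caregiver difference.

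**Working it through.** **1. The plan's own figure.** Inputs from section 4.4: 25% in patients, 5% in caregivers, 95% confidence level, 80% power. With a two-sided test, pooled variance under the null and no continuity correction:

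n = [1.96·√(2·0.15·0.85) + 0.8416·√(0.25·0.75 + 0.05·0.95)]² / 0.20² = (0.990 + 0.408)² / 0.04 = 48.8, so 49 per group.

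This reproduces 49 + 49 (power 80.1%). The point does not alter that calculation.

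**2. Who is covered by what.**

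| Therapy other than ICI | Existing cohort (4.1 description) | Added patients (4.2 and 4.3, ICI as reference point) |
|---|---|---|
| Systemic, before ICI | none | barred |
| Systemic, after ICI | none | barred |
| Systemic, together with ICI | none | not addressed |

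The two sources differ only in the last row.

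**3. Size.** Let a be the share of patients who are additions and c the share of those who were co-treated. Neither is in the documents. The overall co-treated share is f = a·c. Let p0 be the prevalence after ICI alone and q the prevalence in co-treated patients. Then

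patient prevalence = (1 − f)·p0 + f·q, and the shift due to co-treatment = f·(q − p0).

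Take q = 25%, the section 4.4 figure for other cancer survivors, as an assumption:

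| f | p0 = 5% (no ICI effect) | p0 = 15% | p0 = 25% (as planned) |
|---|---|---|---|
| 10% | 7% | 16% | 25% |
| 20% | 9% | 17% | 25% |
| 30% | 11% | 18% | 25% |

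Caregivers stay at 5%. In the first column the shift is 2, 4 and 6 points of the planned 20. To see what f implies: f = 10% arises if 20% of patients are additions and half of those were co-treated; f = 30% arises if 60% are additions and half of those were co-treated.

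If co-treatment adds to an ICI effect, q could exceed 25%. With q = 40% (an assumption) and p0 = 25%, patient prevalence is 0.9·25 + 0.1·40 = 26.5% at f = 10% and 0.7·25 + 0.3·40 = 29.5% at f = 30%.

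**4. Chance of a significant patient excess with no ICI effect.** With 49 per group and p0 = 5%, the chance is Φ[(Δ − 1.96·SE pooled) / SE unpooled]. At f = 10%: Δ = 0.02, SE pooled = √(2·0.06·0.94/49) = 0.0480, SE unpooled = √((0.07·0.93 + 0.05·0.95)/49) = 0.0479, so Φ(−1.54) = 6%. The same formula gives 12% at f = 20% and 19% at f = 30%. With no co-treatment it is Φ(−1.96) = 2.5%, because only one direction is counted. These values are approximate: only 49 × 0.05 = 2.45 affected caregivers are expected. They apply to the comparison of proportions that section 4.4 sizes, not to the score comparisons in section 10.

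**The case against.** **The text may already bar these patients.** Section 4.3 does not say what *previous or subsequent* is measured from. Criterion 1 is listed for caregivers too, who have no ICI date. Measured from study entry, a drug given with an ICI two or more years ago is previous and therefore barred. The criterion also reads as a closed list of allowed therapies, and section 4.1 points to an ICI-only intent. This stands in part: a reader might infer that a co-treated patient certainly passes every criterion, and the documents do not support that certainty. But *subsequent* fits the ICI as reference point better than study entry, and no criterion states the intent. An ambiguous rule that literally admits patients at odds with section 4.1 still needs repair.

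**Exposure is not shown.** The documents name no regimen that combines an ICI with another systemic drug, so a, c and f are all assumptions. This stands.

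**The effect could be small.** A reader might infer that co-treatment could produce half of the planned difference, since f = 50% gives 5 + 20·0.5 = 15%. Only added patients are affected, so this needs at least half of all patients to be additions, and all of those co-treated if exactly half are. It also needs no ICI effect and a 25% rate borrowed from other cancers. The documents do not support it as a working scenario.

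**The objective is prevalence, not cause.** A reader might infer that the dysfunction will be counted as an ICI effect. The primary objective only compares prevalence after ICI with caregivers, although the rationale discusses these changes as adverse events of ICI. Patients also differ from caregivers in having had cancer and possibly surgery or radiotherapy, so even the amended criterion would not isolate ICI. That limits the claim, but the prevalence would still describe a group other than the one in section 4.1.

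**Conclusion.** The point holds as an inconsistency between section 4.1 and the listed criteria. It affects added patients only, and it rests on reading the ICI as the reference point in criterion 1. On that reading, added patients who had systemic therapy together with the ICI are eligible, and any lasting effect of that therapy enters the unadjusted comparison.

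The size cannot be determined from the documents. With no ICI effect and the protocol's own rates, the patient prevalence would be 7% at an overall co-treated share of 10% and 11% at 30%, against 5% in caregivers. If the ICI-only rate is the planned 25% and co-treated patients have the same rate, the shift is zero. The documents show neither that co-treated patients will enter nor that a bias of any given size will arise. The case for acting is that the gap is easy to close and the planned analysis has no means of handling it.

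**What to change.** Reconcile sections 4.1 and 4.3. Add to exclusion criterion 1, for patients, that the section 4.1 restriction on other systemic anticancer treatment also covers treatment given concurrently with the ICI. Keep the existing parenthesis on radiotherapy in the head-neck and brain region, and leave criterion 4 as it is. A full rewrite of criterion 1 that lost the parenthesis would weaken the protection of taste, smell and saliva, because criterion 4 is limited to palliative radiotherapy for bone metastasis. With the added sentence, the missing reference point no longer matters for patients.

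If co-treated patients are already enrolled, record the concurrent agents from the patient file, base the primary patient-caregiver comparison on patients without them, and report the full set as a sensitivity analysis.

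The cost is a one-sentence protocol amendment and a file check. Somewhat fewer added patients will be eligible. The size of the existing cohort (70-120) does not remove this cost: only those who permitted renewed contact and now consent will take part, and section 4.1 plans additions to reach the required number. Recruitment may therefore be slower, or the primary comparison may have fewer than 49 patients.

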4.4 Sample size calculation

It is expected that long-term taste and smell dysfunction are prevalent in 25% of the patients. As described in the introduction, taste changes were found in 24% of patients using immunotherapy(9). In this study, however, it is not reported whether these changes were reported spontaneously or were actively asked. It is therefore possible that the percentage of 24% will be even higher. From earlier studies in patients years after treatment of testis carcinoma or childhood cancer, it is know that about 25% of these (former) patients have long-term taste and smell changes(21,22). Based on this information, the percentage of 25% was determined.

As caregivers with a history of disorders affecting taste and smell will be excluded, it is expected that these dysfunctions are present in 5% of the caregivers. If so, the differences between the patient and control group of caregivers can be assessed in a cohort of in total 49+49=98 patients and caregivers with a 95% confidence level and a power of 80%.

5. TREATMENT OF SUBJECTS

Not applicable

6. INVESTIGATIONAL PRODUCT

Not applicable.

7. INVESTIGATIONAL PRODUCT

Not applicable.

8. METHODS

8.1 Study parameters/endpoints

8.1.1 Main study parameter/endpoint

Taste and smell dysfunction measured using taste strips and Sniffin' Sticks in patients compared to caregivers.

8.1.2 Secondary study parameters/endpoints

- Salivary flow rate
- Salivary pH
- Salivary electrolytes and protein concentrations
- Perceived taste and smell dysfunction
- Perceived xerostomia (XI-scores and RODI-scores)

8.2 Study procedures

Both patients and caregivers are asked not to smoke, brush teeth, eat, or drink anything except water one hour before the tests. Then, unstimulated and chewing-stimulated saliva will be collected, the salivary flow rate will be measured using standardized procedures, and patients and caregivers will fill in two questionnaires regarding perceived taste and smell dysfunction. Taste and smell dysfunction will be assessed with taste strips and Sniffin' Sticks. To assess subjective taste and smell perception, and the impact of taste and smell dysfunction, the Chemotherapy-induced Taste Alteration Scale (CiTAS) questionnaire, the Patient-Generated Subjective Global Assessment (PG-SGA) questionnaire, the Appetite, Hunger and Sensory Perception (AHSP) and the Questionnaire of Olfactory Disorders (QOD) will be used. Subjective xerostomia will be assessed with the Dutch versions of the Xerostomia Inventory (XI) and the Regional Oral Dryness Inventory (RODI). The results of the patients will be compared with the caregivers. Salivary flow rate and pH will be measured immediately after collection, and subsequently the saliva will be stored at -80°C until biochemical analysis. Below, the tests and examinations are explained in more detail.

Taste dysfunction

Taste dysfunction will be objectively measured with "Taste Strips" (Burghart, Wedel, Germany)(23). Strips with an impregnated taste solution will be placed on the participants' tongue. The taste solutions contain the basic tastes bitter, sweet, sour and salty in four different concentrations, thus 16 tests will be performed. The strips will be randomly administered and participants are asked which taste they notice. A right answer gives one point and a total of 16 point can be obtained.

Smell dysfunction

Smell dysfunction will be objectively measured with "Sniffin' Sticks" (Burghart, Wedel, Germany)(24). Pens filled with liquid odorants are presented to the participants' nose. Participants will smell 16 different scents with an interval of minimal 30 seconds to

prevent desensitization. For each scent, participants will choose between four options from a multiple choice card. Smell threshold will be measured with "Sniffin' Sticks" with different odor concentrations.

Saliva (flow rate, pH and elektrolytes)

Saliva flow will be measured, both stimulated and unstimulated(25). The pH of saliva will be determined immediately after collection using an electronic pH meter. The composition of the saliva is determined by measuring electrolyte concentration (Na, K, Cl, HCO₃, Zn) and the enzyme activity/concentrations of chitinase, amylase, lysozyme, Mucin5B, total protein, and carbonic anhydrase.

Questionnaires

Dysfunction in taste will be subjectively measured with the validated Dutch version of the CiTAS questionnaire(26). The CiTAS questionnaire consists of 18 questions on a 5-point Likert-scale and identifies the type and severity of taste dysfunction. The PG-SGA assesses weight, food intake, symptoms, and activities and function in 8 questions(27). The AHSP questionnaire consists of 29 multiple choice questions and assesses appetite, hunger and sensory perception(28). Impact on quality of life will be measured with the QOD questionnaire(29). Xerostomia will be quantified with the internationally validated XI (a questionnaire with 11 items on a 5-point Likert-scale) and the RODI(30,31). The RODI consists of a schematic representation of 9 intra-oral areas, and the patient can indicate the severity of the xerostomia at these areas on a 5-point Likert scale.

8.3 Withdrawal of individual subjects

Subjects can leave the study at any time for any reason if they wish to do so without any consequences. The investigator can decide to withdraw a subject from the study for urgent medical reasons.

8.3.1 Specific criteria for withdrawal

Occurrence of signs or symptoms of progressive disease during study visit (after informed consent was signed).

8.4 Follow-up of subjects withdrawn from treatment

Subjects withdrawn from the study will not be assessed at a later time.

9. SAFETY REPORTING

9.1 Temporary halt for reasons of subject safety

In accordance to section 10, subsection 4, of the WMO, the sponsor will suspend the study if there is sufficient ground that continuation of the study will jeopardise subject health or safety. The sponsor will notify the accredited METC without undue delay of a temporary halt including the reason for such an action. The study will be suspended pending a further positive decision by the accredited METC. The investigator will take care that all subjects are kept informed.

9.2 AEs, SAEs and SUSARs

9.2.1 Adverse events (AEs)

Adverse events are defined as any undesirable experience occurring to a subject during the study, whether or not considered related to the study procedure. All adverse events reported spontaneously by the subject or observed by the investigator or his staff will be recorded.

9.2.2 Serious adverse events (SAEs)

A serious adverse event is any untoward medical occurrence or effect that

- results in death:
- is life threatening (at the time of the event);
- requires hospitalisation or prolongation of existing inpatients' hospitalisation;
- results in persistent or significant disability or incapacity;
- is a congenital anomaly or birth defect; or
- any other important medical event that did not result in any of the outcomes listed above due to medical or surgical intervention but could have been based upon appropriate judgement by the investigator.

An elective hospital admission will not be considered as a serious adverse event.

The sponsor will report the SAEs through the web portal *ToetsingOnline* to the accredited METC that approved the protocol, within 7 days of first knowledge for SAEs that result in death or are life threatening followed by a period of maximum of 8 days to complete the initial preliminary report. All other SAEs will be reported within a period of maximum 15 days after the sponsor has first knowledge of the serious adverse events.

9.3 Follow-up of adverse events

All AEs will be followed until they have abated, or until a stable situation has been reached. Depending on the event, follow up may require additional tests or medical procedures as indicated, and/or referral to the general physician or a medical specialist. SAEs need to be reported till end of study within the Netherlands, as defined in the protocol.

10. STATISTICAL ANALYSIS

This study aims to investigate the prevalence of taste and smell dysfunction in a predefined cohort of melanoma, NSCLC and urogenital cancer patients. Results will be reported as mean (standard deviation) and median (range) for parametric and non-parametric continuous variables, respectively. Categorical data will be presented as N and percentages.

Participants and their caregivers will be compared using Mann Whitney U test or independent T-test, depending on data distribution. For ordinal data, Chi-square tests will be performed. Correlations between perceived and objective taste and smell dysfunction will be studied with Pearson's rho or Spearman's rho, depending on data distribution.

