2. OBJECTIVES

Primary Objective:

• To determine the prevalence of taste and smell dysfunction in patients more than two years after start of ICI therapy - compared with a control group of caregivers.

Secondary Objective(s):

- To assess the association between taste and smell dysfunction, and saliva secretion rate, saliva composition (pH, electrolyte and protein composition) and subjective feeling of a dry mouth (xerostomia) in patients more than two years after start of ICI therapy compared with a control group of caregivers.
- To assess the impact of taste and smell dysfunction in patients more than two years after start of ICI therapy.

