3. STUDY DESIGN

In this cross-sectional study, patients with melanoma, NSCLC or urogenital cancer ≥ 2 years following ICI therapy and their caregivers will be included. We will include patients who have previously participated in the study "Quality of life, cognitive function, and physical fitness of patients surviving more than 2 years after immune checkpoint inhibitor therapy" (METc 2018/158, clinicaltrials.gov NCT03946007) and additional patients who are under control at the departments of Medical Oncology and Pulmonary Disease and did not participate in this previous studyA patient cohort of 70-120 patients and 70-120 of their caregivers has already been built and patients who have given permission to be approached for future research again will be invited for our study.

Patients can be approached in two ways: 1) Patients will be asked during an outpatient clinic appointment by their clinical doctor if they can be approached afterwards by the investigator. When permission is given, the investigator will explain the study design and give the patient and the caregiver both a letter. These letters explains the study design and includes an informed consent form, 2) Patients who do not have an outpatient clinic appointment in the near future will be sent the letter with the study design and the informed consent form. In this letter, we will also ask each participant to invite their caregiver to participate in this study. For this, a separate letter directed at the caregiver will be sent to the participant. Patients and caregivers are asked to contact the investigator team if they are willing to participate. If the patient consents, a single appointment will be made during a regular follow-up visit to the outpatient clinic. If the caregiver consents too, we will make an appointment with both participants at the same time, if possible. Patients can participate alone if the caregiver is not willing to participate, and vice versa.

During this visit, if patients and caregivers have no questions regarding the study or the study information that was sent, they are first asked to sign the informed consent. Next, saliva will be collected, and taste, smell and dry mouth will be subjectively and objectively be measured. Afterwards, characteristics will be taken from the patients' electronic file, including age, gender, medical history and medication use. As the caregivers do not have a medical file, they are asked for these characteristics.

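### The planned patient-caregiver comparison makes no allowance for age or sex, although the groups are unmatched and both variables are recorded

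*Combined protocol and SAP*

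**What the plan says.** The primary objective (section 2) is "To determine the prevalence of taste and smell dysfunction in patients more than two years after start of ICI therapy", set against a caregiver control group. Section 8.1.1 repeats the contrast, and section 4.4 sizes the study on it.

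- **Analysis.** Section 10: "Participants and their caregivers will be compared using Mann Whitney U test or independent T-test, depending on data distribution". Chi-square is added for ordinal data. Section 10.1 adds only descriptive summaries of the taste and smell scores. No regression, stratified, matched or standardised analysis appears.
- **Choice of controls.** Section 4.1: "The caregivers will act as control group for practical purposes". It also argues that "caregivers tend to have the same basic characteristics as the patients, and therefore, these characteristics will be distributed more equally in both groups".
- **Eligibility.** Under "A caregiver must meet all of the following criteria", section 4.2 lists adulthood, understanding of the procedures and consent. Neither this list nor the exclusions in 4.3 relates a caregiver's age or sex to the patient's.
- **Pairing.** Section 3: "Patients can participate alone if the caregiver is not willing to participate, and vice versa".
- **Data collected.** Section 3: "characteristics will be taken from the patients' electronic file, including age, gender, medical history and medication use"; and for caregivers, "As the caregivers do not have a medical file, they are asked for these characteristics".

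**The concern.** Patients and caregivers are two self-selected groups. A two-sample test asks whether they differ. It cannot say whether a difference belongs to being a long-term survivor after immune checkpoint inhibitor (ICI) therapy or to a different mix of ages and sexes. The protocol treats similar basic characteristics as a merit of its control group, but it neither enforces that similarity nor corrects for its absence.

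What is at stake is the comparison half of the primary objective. A gap in age or sex could create, enlarge, shrink or hide a patient-caregiver difference, provided that these variables matter for the tests used. The variables needed to deal with this will already be in the database.

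**Working it through.** **1. The plan's own figure.** Section 4.4 gives 25% against 5%, 95% confidence, 80% power and 49 per group. The pooled two-sided two-proportion formula, with mean proportion 0.15, is

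n = [1.96·√(2·0.15·0.85) + 0.8416·√(0.25·0.75 + 0.05·0.95)]² / 0.20² = (0.990 + 0.408)² / 0.04 ≈ 48.8, so 49 per group (power 80.1%).

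The figure reproduces. The formula is unadjusted and unpaired, like the tests in section 10.

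**2. Assumptions.** The documents give no age or sex distribution by group and no age or sex effect. Everything below is therefore assumed, apart from 49 per group:
- age effect 0.02 SD per year; age SD 10 years; gap 5 years, giving 5 × 0.02 = 0.10 SD
- sex effect 0.3 SD; gap 30 percentage points, giving 0.30 × 0.3 = 0.09 SD
- net bias 0.10 + 0.09 = 0.19 SD if the gaps act in the same direction (aligned), and 0.10 − 0.09 = 0.01 SD if they oppose
- 35 patient-caregiver pairs plus 14 + 14 people taking part alone; within-pair correlation 0.2.

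**3. Scores, by formula.** For independent groups, a bias of b SD gives the t-test (96 df) a noncentrality of b·√(49/2) = 4.95·b.

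| Net bias (SD) | 0 | 0.1 | 0.2 | 0.3 |
|---|---|---|---|---|
| False-positive rate | 5.0% | 7.8% | 16.5% | 31.2% |

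**4. Scores, by simulation with pairs** (40,000 runs per cell). The adjusted model is linear in group, age and sex, with standard errors clustered by pair. The true difference used for the estimates and power is 0.57 SD, which 49 per group detect with 80% power.

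| | No gap | Aligned | Opposed |
|---|---|---|---|
| False positives, t-test | 3.7% | 12.8% | 3.6% |
| False positives, adjusted | 4.9% | 5.4% | 5.2% |
| Mean estimate, t-test | 0.57 | 0.76 | 0.58 |
| Mean estimate, adjusted | 0.57 | 0.57 | 0.57 |
| Power, adjusted | 84% | 77% | 78% |

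Without gaps the t-test has 79% power.

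**5. Why the t-test falls below 5% without a gap.** It ignores positive within-pair correlation, so its standard error is too large by the factor 1/√(1 − (35/49)·0.2) = 1.08.

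**6. Prevalence.** Section 10 names chi-square for ordinal data and assigns no test to yes/no dysfunction; Pearson chi-square is taken as the nearest planned test. The simulation uses the same age and sex effects on an underlying scale, with a true prevalence of 15% in both groups.

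| | No gap | Aligned | Opposed |
|---|---|---|---|
| Spurious difference (points) | 0 | 4.3 | 0.2 |
| Chi-square rejects | about 5% | about 9% | about 5% |

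With a true 25% against 5% (20 points), the expected unadjusted difference is 20.0, 23.8 and 20.2 points. An age- and sex-standardised estimate averages 20.0, 19.7 and 19.8.

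**7. Events available for adjustment.** 49 × 0.25 + 49 × 0.05 = 12.25 + 2.45 = 14.7, about 15.

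**The case against.** **Two assumptions are stacked.** No section says that age or sex affects taste or smell scores, and none shows an imbalance. Section 4.1 addresses comparability through the choice of controls. This stands: the bias is a possibility, its size is unknown, and opposing gaps can cancel. But section 4.1 states an expectation, and nothing in the plan acts if the expectation fails.

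**The larger false-positive figures overstate the case.** The 16.5% and 31.2% assume independent groups, and 0.3 SD exceeds the worked example. This stands; the 13% from the paired simulation is the fairer figure, and it needs both gaps to point the same way.

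**For prevalence, adjustment buys little in error control.** A bootstrap interval around a standardised difference (from a penalised logistic model) wrongly excludes zero in 6.7%, 7.7% and 7.3% of runs with no gap, aligned and opposed gaps. Pearson chi-square rejects in about 5%, 9% and 5%; with continuity correction, in 2.1%, 4.2% and 2.0%. This also stands. With about 15 events, what adjustment offers is mainly a less biased estimate, so it belongs in a sensitivity role.

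**Why only age and sex?** Section 3 also records medical history and medication. Both can be consequences of the cancer or its treatment, and adjusting for them could remove part of the difference of interest. Age and sex cannot be.

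**A stronger reading to avoid.** A reader might infer that ignoring the patient-caregiver link inflates false positives. With positive within-pair correlation it does the opposite: the planned tests become conservative, and only efficiency is lost.

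**Conclusion.** The concern holds as a gap in the analysis plan. The between-group comparison is unadjusted, no rule matches the groups on age or sex, and both variables are available in both groups. If age or sex affects the scores and the groups differ on them, the comparison could be biased in either direction. Under the assumed aligned gaps, the t-test's false-positive rate is about 13% against about 5% adjusted, and a true 0.57 SD is estimated as 0.76. At 15% prevalence in both groups, a spurious difference of about 4 points appears and chi-square rejects in about 9%. With no gap or opposed gaps there is no excess.

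A reader might infer that the groups are in fact imbalanced, or that the patient-caregiver result will be invalid. The documents do not support that: they report no imbalance and no age or sex effect. The prevalence in patients taken alone does not depend on the control group and is untouched, and the sample size of 49 per group is correct for its stated inputs.

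**What to change.** Amend section 10 before the analysis:

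1. **Scores** (taste, smell identification, smell threshold). Make the main between-group comparison a linear model with group, age and sex, with standard errors clustered by patient-caregiver pair. A person taking part alone is their own cluster. Report the planned unadjusted tests alongside, and tabulate age and sex by group.
2. **Dysfunction yes/no.** Fix the cut-off first, since the documents state none. Keep the two unadjusted prevalences and their difference as the main result. Add one prespecified age- and sex-adjusted difference, labelled a sensitivity estimate because only about 15 events are expected. Leave out of the adjustment any variable already built into the cut-off.
3. **Data.** Record a pair identifier.

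Cost: a protocol amendment under section 12.3, the identifier and slightly more analysis work; age and gender are already collected. If the groups do differ, the score comparison loses a little power (77-78% in the example, against 79% for the t-test without gaps). If they do not, the adjusted model gains (84%). The adjusted yes/no estimate will have limited stability; in the example its bootstrap interval covers 92-94% rather than 95%.
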